4.5.3 Physical Examinations and Assessments

A complete physical examination should include an evaluation of the head, eyes, ears, nose, and throat and the cardiovascular, dermatological, musculoskeletal, respiratory, gastrointestinal, genitourinary, and neurological systems. Any abnormality identified at baseline should be recorded on the General Medical History and Baseline Conditions eCRF.

The Lansky Performance Status should be performed for patients who are < 16 years old, and the Karnofsky Performance Status should be performed for patients who are ≥ 16 years old.

At subsequent visits (or as clinically indicated), changes from baseline abnormalities should be recorded in patient notes. New or worsened clinically significant abnormalities should be recorded as adverse events on the Adverse Event eCRF.

Fractional shortening or LVEF should be determined within 28 days prior to initiation of study drug by either echocardiography or MUGA scan.

During the treatment period, weight will be measured at the beginning of each cycle. During the follow-up period, weight should be measured every 3 months for the first 2 years, every 6 months during the 3rd year, and yearly thereafter.

During the treatment period, height, head circumference (until the age of 3 years), and Tanner stage should be measured every four cycles (approximately every 3 months). During the follow-up period, height, head circumference, and Tanner stage should be measured every 3 months for the first 2 years, every 6 months during the 3rd year, and yearly thereafter. Tanner staging should be performed until the patient has reached Tanner Stage V.

4.5.3.1 *Neurologic Examinations (ATRT Only)*

For patients with ATRT, a complete neurologic examination should be completed at every patient visit, including at baseline (see Schedule of Assessments in [Appendix 1](#)). Any abnormality identified at baseline should be recorded on the General Medical History and Baseline Conditions eCRF.

At subsequent visits (or as clinically indicated), changes from baseline abnormalities need to be reviewed carefully prior to administering the next atezolizumab dose.

Atezolizumab should not be administered if there is any sign of increased intracranial pressure.

The neurologic examination should include age-appropriate evaluations of vision, including visual fields, coordination, cranial nerve function, strength and motor evaluations (including gait when appropriate), and reflexes. Discussions with the parents and/or guardian should also occur to assess for new or worsening symptoms, including but not limited to changes in physical activity, irritability, headaches, changes in appetite and/or feeding, vomiting, and nausea.

New or worsened clinically significant abnormalities should be recorded as adverse events on the Adverse Event eCRF.

4.5.4 Vital Signs

Age-appropriate equipment should be used to obtain vital signs and assessments and adjusted for growth. Vital signs will include measurements of respiratory rate, pulse rate, systolic and diastolic blood pressures, oxygen saturation by pulse oximetry, and temperature.

For the first infusion of atezolizumab, vital signs should be determined within 60 minutes before, every 15 (± 5) minutes during, and 30 (± 10) minutes after the end of infusion. For subsequent infusions, vital signs should be recorded within 60 minutes before infusion and at the end of infusion (± 10) minutes, but vital signs do not need to be obtained during the infusion if the prior infusion was tolerated without symptoms.

4.5.5 Tumor and Response Evaluations

4.5.5.1 Tumor Assessments

All known sites of disease must be documented at screening and re-assessed at each subsequent tumor evaluation. Baseline tumor assessments should be performed within 28 days prior to initiation of study drug (Day 1 of Cycle 1). Tumor assessments must be performed during the last week of Cycles 2, 4, 6, and 8 and every 4th cycle thereafter (i.e., within 7 days prior to Day 1 of the next cycle). At the investigator's discretion, unscheduled tumor assessments may be performed at any time if progressive disease is suspected. For patients who continue treatment beyond radiographic progressive disease because of possible pseudoprogression, a follow-up scan must be performed after 2 cycles or earlier if clinically indicated.

Response will be assessed by the investigator on the basis of physical examinations, CT scans, MRI scans, fluorodeoxyglucose-positron emission tomography (FDG-PET) scans, or MIBG scans, as appropriate. *Tumor assessment imaging should include all areas of known disease. A chest CT is also required to be performed at each assessment.* An objective response should be confirmed by repeat assessments ≥ 4 weeks after initial documentation. The same *imaging techniques and procedures* used to assess disease sites at screening should be used throughout the study (e.g., the same contrast protocol

for CT scans). To the extent that is feasible, assessments should be performed by the same evaluator to ensure internal consistency across visits.

Patients with neuroblastoma must have a MIBG scan and bilateral bone marrow aspirates and/or biopsies done for disease evaluation. If the enrollment bone marrow aspirates and/or biopsy tissue samples are negative for disease, subsequent bone marrow aspirates and/or biopsy tissue samples are not needed. Patients with evidence of bone marrow disease at screening require bone marrow evaluation with scheduled disease evaluations until they have had two consecutive evaluations that are negative for disease. Patients with neuroblastoma should also have urine catecholamine test results (including homovanillic acid and vanillylmandelic acid) sent at screening and with all responses assessments.

Patients with lymphoma should undergo FDG-PET imaging at screening and with each response assessment. For lymphoma patients with a clinical suspicion of bone marrow involvement, bilateral bone marrow aspirates and/or biopsies should be performed at screening. Patients who have documented bone marrow involvement at screening should have subsequent bilateral bone marrow evaluations performed with each response assessment until the first negative bone marrow evaluation.

Patients without neuroblastoma or lymphoma who have a clinical suspicion of bone marrow involvement should also have bilateral bone marrow aspirates and/or biopsies performed at screening. Patients who have documented bone marrow involvement at screening should have subsequent bone marrow evaluations performed with each response assessment until the first negative bone marrow evaluation.

4.5.5.2 Response Criteria

All tumors will be evaluated for disease response and progressive disease with RECIST v1.1 (see [Appendix 6](#)) with the exception of those listed below.

- Neuroblastoma: *m*INRC (see [Appendix 3](#))
- Hodgkin's lymphoma and non-Hodgkin's lymphoma: Revised Response Criteria for Malignant Lymphoma (see [Appendix 4](#))
- ATRT: RANO criteria (see [Appendix 11](#))

Patients with synchronous ATRT and rhabdoid tumor with no clear primary should be enrolled into the rhabdoid tumor cohort. These patients' tumors will be evaluated with RECIST v1.1 criteria.

Patients who enroll with evaluable but not measurable disease will have a modified response assessment. For such patients, partial response cannot be determined; therefore, response will be limited to complete response, stable disease, or progressive disease.

During treatment, patients who show evidence of clinical benefit will be permitted to continue atezolizumab treatment after criteria for progressive disease for their specified response assessment are met, if they meet all of the following criteria:

- Evidence of clinical benefit as assessed by the investigator and agreed upon by the Medical Monitor
- Absence of symptoms or signs (including worsening laboratory test values) indicating unequivocal progression of disease
- No decline in Lansky or Karnofsky Performance Status that can be attributed to disease progression
- Absence of tumor progression at critical anatomical sites (e.g., leptomeningeal disease) that cannot be managed by protocol-allowed medical interventions

Patients and/or their parents or guardians must sign a consent acknowledging treatment continuation after possible worsening disease in order to continue to receive atezolizumab. Patients for whom radiographic disease progression is confirmed at a subsequent tumor assessment may be considered for continued study treatment at the discretion of the investigator if they have evidence of clinical benefit and continue to meet the criteria above. If an individual patient continues to experience clinical benefit beyond 2 years of radiologic progressive disease (see Section 3.3.4), the Sponsor and treating physician will apply for additional approval from health authorities for continued treatment.

Collection of an optional tumor biopsy sample, if clinically feasible, at the time of first radiographic progression on atezolizumab treatment is encouraged in order to evaluate the utility of the biopsy tumor sample in distinguishing pseudoprogression or tumor immune infiltration from true progressive disease.

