- Atezolizumab minimum serum concentration (C_{min}) prior to the infusion on Day 1 of Cycles 2, 3, 4, 8, 12, and 16 and every 8 cycles thereafter
- Atezolizumab serum concentration at washout (90 or more days after the last dose)
- Atezolizumab area under the concentration-time curve for serum concentration-time profile in Cycle 1 will be estimated using a population PK model, as appropriate.

Immunogenicity Outcome Measure

The immunogenicity outcome measure for this study is as follows:

- Incidence of ATAs during the study relative to the prevalence of ATAs at baseline

Efficacy Outcome Measures

The primary efficacy outcome measures for this study are as follows:

- Objective response, defined as a complete or partial response for patients with measurable disease or neuroblastoma patients with evaluable disease at baseline, or a complete response for patients with non-measurable but evaluable disease at baseline (except patients with neuroblastoma) on two consecutive occasions ≥ 4 weeks apart, as determined by the investigator using RECIST v1.1 for patients with solid tumors, *mINRC* for patients with neuroblastoma, Revised Response Criteria for Malignant Lymphoma for patients with Hodgkin's lymphoma or non-Hodgkin's lymphoma, and *RANO criteria for patients with ATRT*.
- Clinical benefit response, defined as objective response or stable disease for at least 6 months, as determined by RECIST v1.1 for patients with osteosarcoma
- PFS, defined as the time from initiation of study drug to the first documented occurrence of progressive disease, as determined by the investigator using RECIST v1.1 for patients with solid tumors, *mINRC* for patients with neuroblastoma, Revised Response Criteria for Malignant Lymphoma for patients with Hodgkin's lymphoma or non-Hodgkin's lymphoma, and *RANO criteria for patients with ATRT*, or death from any cause, whichever occurs first

The secondary efficacy outcome measures for this study are as follows:

- DOR, defined as the time from the first tumor assessment that supports the patient's objective response to the time of progressive disease, as determined by the investigator using RECIST v1.1 for patients with solid tumors, *mINRC* for patients with neuroblastoma, Revised Response Criteria for Malignant Lymphoma for patients with Hodgkin's lymphoma or non-Hodgkin's lymphoma, and *RANO criteria for patients with ATRT*, or death from any cause, whichever occurs first

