3.4.4 Efficacy Outcome Measures

The primary efficacy outcome measures for this study are as follows:

- Objective response, defined as a complete or partial response for patients with measurable disease or neuroblastoma patients with evaluable disease at baseline, or a complete response for patients with non-measurable but evaluable disease at baseline (except patients with neuroblastoma) on two consecutive occasions ≥ 4 weeks apart, as determined by the investigator using RECIST v1.1 for patients with solid tumors (see [Appendix 6](#)), *m*INRC for patients with neuroblastoma (see [Appendix 3](#)), Revised Response Criteria for Malignant

Lymphoma for patients with Hodgkin's lymphoma or non-Hodgkin's lymphoma (see [Appendix 4](#)), and RANO criteria (see [Appendix 11](#)) for patients with ATRT.

- Clinical benefit response (CBR), defined as objective response or stable disease for at least 6 months, as determined by RECIST v1.1 for patients with osteosarcoma (see [Appendix 6](#))
- PFS, defined as the time from initiation of study drug to the first documented occurrence of progressive disease, as determined by the investigator using RECIST v1.1 for patients with solid tumors (see [Appendix 6](#)), mINRC for patients with neuroblastoma (see [Appendix 3](#)), Revised Response Criteria for Malignant Lymphoma for patients with Hodgkin's lymphoma or non-Hodgkin's lymphoma (see [Appendix 4](#)), and RANO criteria (see [Appendix 11](#)) for patients with ATRT, or death from any cause, whichever occurs first

The secondary efficacy outcome measures for this study are as follows:

- DOR, defined as the time from the first tumor assessment that supports the patient's objective response to the time of progressive disease, as determined by the investigator using RECIST v1.1 for patients with solid tumors (see [Appendix 5](#)), mINRC for patients with neuroblastoma (see [Appendix 3](#)), Revised Response Criteria for Malignant Lymphoma for patients with Hodgkin's lymphoma or non-Hodgkin's lymphoma (see [Appendix 4](#)), and RANO criteria ([Appendix 11](#)) for patients with ATRT, or death from any cause, whichever occurs first
- OS, defined as the time from initiation of study drug to death from any cause

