- In exceptional cases of patients with relapsed pediatric tumors who are ≥ 30 years of age, the Sponsor will consider waiving the age requirement with approval of the Medical Monitor. This waiver is restricted to patients with pediatric-specific diseases (e.g., neuroblastoma), for whom clinical trials are unlikely to be available, and will not be extended to patients with tumors that typically occur both in children and adults (i.e., high-grade glioma).
- Able to comply with the study protocol, in the investigator's judgment
- Weight is ≥ 3 kg
- Disease that is measurable as defined by RECIST v1.1, mINRC, Revised Response Criteria for Malignant Lymphoma, or RANO criteria (as appropriate) or evaluable by nuclear medicine techniques, immunocytochemistry techniques, tumor markers, or other reliable measures
- Archival tumor tissue block or 15 freshly cut, unstained, serial slides available for submission or willingness to undergo a core or excisional biopsy prior to enrollment (fine-needle aspiration, brush biopsy, and lavage samples are not acceptable)
 - Patients with fewer than 15 slides available may be eligible for study entry following discussion with the Medical Monitor. See Section 4.5.6 for detailed tissue requirements.
- Lansky Performance Status (patients who are < 16 years old) or Karnofsky Performance Status (patients who are ≥ 16 years old) ≥ 50 (see [Appendix 8](#) and [Appendix 9](#))

- Life expectancy is ≥ 3 months, in the investigator's judgment
- For patients of childbearing potential: agreement to remain abstinent (refrain from heterosexual intercourse) or use two adequate methods of contraception, including at least one method with a failure rate of $< 1\%$ per year, during the treatment period and for at least *5 months* after the last dose of study drug

Examples of contraceptive methods with a failure rate of $< 1\%$ per year include established, proper use of hormonal contraceptives that inhibit ovulation, hormone-releasing intrauterine devices (IUDs), and copper IUDs.

The reliability of sexual abstinence should be evaluated in relation to the duration of the clinical trial and the preferred and usual lifestyle of the patient. Periodic abstinence (e.g., calendar, ovulation, symptothermal, or postovulation methods) and withdrawal are not acceptable methods of contraception.

Barrier methods must always be supplemented with the use of a spermicide.

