6.6.1 Primary Efficacy Endpoint

The primary endpoints for efficacy are ORR and PFS. For patients with measurable disease or patients with neuroblastoma who have evaluable disease at baseline, an objective response is defined as a complete or partial response on two consecutive occasions ≥ 4 weeks apart, as determined by the investigator using RECIST v1.1 for patients with solid tumors (see [Appendix 6](#)), *mINRC* for patients with neuroblastoma (see [Appendix 3](#)), Revised Response Criteria for Malignant Lymphoma for patients with Hodgkin's lymphoma or non-Hodgkin's lymphoma (see [Appendix 4](#)), and *RANO criteria* (see [Appendix 11](#)) for patients with ATRT.

For patients with non-measurable but evaluable disease at baseline (except *patients with neuroblastoma*), an objective response is defined as a complete response on two consecutive occasions ≥ 4 weeks apart, as determined by the investigator using RECIST v1.1 for patients with solid tumors (see [Appendix 6](#)), Revised Response Criteria for Malignant Lymphoma for patients with Hodgkin's lymphoma or non-Hodgkin's lymphoma (see [Appendix 4](#)), and *RANO criteria* (see [Appendix 11](#)) for patients with ATRT.

ORR is the percentage of patients who are determined to have an objective response. Patients with no post-baseline tumor assessments will be counted as non-responders. ORR and corresponding 95% exact CI using the Blyth–Still–Casella method will be summarized overall and by tumor type cohort (except for the osteosarcoma tumor type cohort).

CBR is defined as objective response or stable disease for at least 6 months, as determined by RECIST v1.1 for patients with osteosarcoma (see [Appendix 6](#)). CBRR is the percentage of patients who are determined to have a CBR. Patients with no post-baseline tumor assessments will be counted as not having CBR. CBRR and corresponding 95% CI will be summarized for the osteosarcoma tumor type cohort only.

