Appendix 2 Schedule of Pharmacokinetic, Pharmacodynamic, and Immunogenicity Assessments

Visit	Timepoint	Sample Type
Cycle 1, Day 1	Prior to the infusion	Serum for atezolizumab PK and ATA ^a EDTA plasma and whole blood for PD
	30 (± 10) min after the end of the infusion	Serum for atezolizumab PK
Cycle 1, Day 8	Any time during visit	Serum for atezolizumab PK
Cycle 2, Day 1	Prior to the infusion ^b	Serum for atezolizumab PK and ATA ^a Plasma and whole blood for PD
Cycle 3, Day 1	Prior to the infusion ^b	Serum for atezolizumab PK and ATA ^a Plasma and whole blood for PD
Cycle 4, Day 1	Prior to the infusion ^b	Serum for atezolizumab PK and ATA ^a
	30 (± 10) min after the end of the infusion	Serum for atezolizumab PK
Cycle 8, Day 1	Prior to the infusion ^b	Serum for atezolizumab PK and ATA ^a Plasma and whole blood for PD
Cycle 12, Day 1	Prior to the infusion ^b	Serum for atezolizumab PK and ATA ^a Plasma and whole blood for PD
Day 1 of Cycle 16 and every 8 cycles thereafter	Prior to the infusion ^b	Serum for atezolizumab PK and ATA ^a Plasma and whole blood for PD
Study drug discontinuation visit	Any time during visit	Serum for atezolizumab PK and ATA ^a Plasma and whole blood for PD
At least 90 days (but no more than 150 days) after last dose of study drug	Any time during visit	Serum for atezolizumab PK and ATA ^a Plasma and whole blood for PD

ATA=anti-therapeutic antibody; PD=pharmacodynamic; PK=pharmacokinetic.

^a Serum samples will be split into 2 × 500 µL serum aliquots, one for PK and one for ATA.

^b Blood draws can occur up to 2 days prior to infusion.

Appendix 3

Modified International Neuroblastoma Response Criteria

Below response assessment is modified from the original INRC publication in 1993.

DEFINITION OF MEASURABLE (EVALUABLE) DISEASE ON CT/MRI SCAN

The presence of at least one lesion that can be accurately measured in at least one dimension with the longest diameter at least 20 mm. With a spiral CT scan, lesions must be at least 10 mm. The investigator will identify up to 10 measurable target lesions to be followed for response. Note that bone lesions will be considered as non-target lesions for evaluation of CT/MRI response since they will be evaluated with MIBG scans.

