Patient may be declared to have PD in bone marrow after only one diagnostic bone marrow at the discretion of the treating physician
Patients who enter study with bone marrow tumor by morphology will be considered to have PD if there is a minimum of 25% tumor in the marrow by morphology and a doubling in the amount of tumor in the marrow compared with the level present at study entry. For example, a patient entering with 5% tumor in marrow by morphology must increase to >25% tumor to have PD; a patient entering with 30% tumor must increase to >60% tumor.
- SD: Persistence of an amount of tumor in the bone marrow by morphology that does not meet criteria for either CR or PD
Patients who clear morphologic tumor but have immunocytologic tumor will be called SD.

RESPONSE CRITERIA FOR MIBG-POSITIVE LESIONS

All patients with known MIBG-avid lesions will be evaluable for MIBG response following the first course of therapy. The following criteria will be used to report MIBG response:

- CR: Complete resolution of all MIBG-positive lesions
- PR: Resolution of at least one MIBG-positive lesion, with persistence of other MIBG positive lesions
- SD: No change in MIBG scan in number of positive lesions (includes patients who have same number of positive lesions but decreased intensity)
- PD: Development of new MIBG-positive lesions

Appendix 3

International Neuroblastoma Response Criteria (cont.)

DEFINITION OF OVERALL RESPONSE FOR EACH PATIENT WITH NEUROBLASTOMA

The International Neuroblastoma Response Criteria were developed to define responses in patients being treated with frontline therapy from diagnosis.¹ These criteria were utilized as a basis for the following response criteria, which integrate response at all sites defined as measurable in this study, including CT/MRI lesions that meet RECIST criteria, MIBG-positive lesions, and bone marrow disease. These criteria will be used to define the overall response for each patient.

- CR: Disappearance of all target lesions; no evidence of tumor at any site (chest, abdomen, liver, bone, bone marrow, nodes, etc.); homovanillic acid (HVA) and vanillylmandelic acid (VMA) normal

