- VGPR: Greater than 90% decrease of the disease measurement for CT/MRI target lesions, taking as reference the disease measurement done to confirm measurable disease in target lesions at study entry; all preexisting bone lesions with CR by MIBG; MIBG scan can be \pm or CR in soft tissue lesions corresponding to lesions on CT/MRI; CR in bone marrow; no new sites of tumor; HVA/VMA normal
- PR: At least a 30% decrease in the disease measurement for CT/MRI target lesions, taking as reference the disease measurement done to confirm measurable disease in target lesions at study entry; bone marrow with CR; MIBG with either PR or CR in bone lesions; MIBG may be SD or CR in soft tissue lesions corresponding to lesions on CT/MRI; HVA/VMA may still be elevated.
- PD: Any one of the following:
 - At least a 20% increase in the disease measurement for CT/MRI target lesions, taking as reference the smallest disease measurement recorded since the start of treatment
 - Appearance of one or more new lesions or new sites of tumor
 - PD as defined above for either bone marrow or MIBG lesions
- SD: Stable disease by either CT/MRI lesion, bone marrow, or MIBG criteria; no new lesions; no new sites of disease

The overall response as assessed at any particular timepoint based on the various disease sites is summarized in the table below.

¹ Brodeur GM, Pritchard J, Berthold F, et al. Revisions of the international criteria for neuroblastoma diagnosis, staging, and response to treatment. *J Clin Oncol* 1993;11:1466–77.

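### Neuroblastoma with evaluable disease: Section 4.5.5.2 rules out the partial response that Sections 3.4.4 and 6.6.1 count, and Appendix 3 cannot return it without CT/MRI target lesions

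*Combined protocol and SAP*

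**What the plan says.** **The endpoint.** Section 3.4.4, like the synopsis, defines objective response as "complete or partial response for patients with measurable disease or neuroblastoma patients with evaluable disease at baseline". Section 6.6.1 repeats this for "patients with neuroblastoma who have evaluable disease at baseline, an objective response is defined as a complete or partial response". Both sections limit other patients with non-measurable disease to CR and expressly exempt neuroblastoma from that limit. Response is assigned by the investigator using Appendix 3.

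**The assessment rule.** Section 4.5.5.2 names the Appendix 3 criteria for neuroblastoma. It then says of all patients with evaluable but not measurable disease: "For such patients, partial response cannot be determined". Their outcomes are limited to CR, stable disease (SD) and progressive disease (PD).

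**Eligibility.** Section 4.1.1 accepts measurable disease or, as the alternative, disease "evaluable by nuclear medicine techniques, immunocytochemistry techniques, tumor markers, or other reliable measures".

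**Appendix 3.**
- On CT/MRI, "bone lesions will be considered as non-target lesions for evaluation of CT/MRI response since they will be evaluated with MIBG scans".
- The overall response combines sites "defined as measurable in this study", and these include MIBG-positive lesions and marrow disease.
- Overall PR begins with "At least a 30% decrease in the disease measurement for CT/MRI target lesions".
- The only overall-PR row in Table 1 has PR in the CT/MRI column.

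**Expansion.** Table 3 in Section 6.1 gives neuroblastoma a historical rate of 18%, a minimum of 10 patients and a minimum of 3 responders.

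**The concern.** ORR is a primary efficacy endpoint. A neuroblastoma patient with bone or marrow disease only can enter the trial, and Section 6.6.1 means to count that patient's PR. The section that governs assessment says PR cannot be determined, and the criteria used to assign it offer no way to reach it. At stake are the reported ORR for this cohort, its comparability between sites, and the responder count that informs expansion. If the rule is settled only after scans have been read, part of a primary endpoint is defined with results in view.

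**Working it through.** **Step 1: the endpoint sections against the assessment rule.** For neuroblastoma with evaluable disease, the synopsis and Sections 3.4.4 and 6.6.1 give CR or PR. For any evaluable but not measurable disease, Section 4.5.5.2 gives CR, SD or PD. The exception written into the first group is missing from Section 4.5.5.2.

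**Step 2: whom Section 4.5.5.2 covers.** Two readings are possible.
- (a) MIBG-only or marrow-only disease is evaluable, not measurable. Section 4.1.1 lists nuclear-medicine disease as the alternative to measurable disease. Sections 3.4.4 and 6.6.1 keep a separate evaluable category for neuroblastoma.
- (b) MIBG and marrow sites are measurable, as the overall-response text of Appendix 3 says. Section 4.5.5.2 then does not reach these patients, and Appendix 3 alone decides.

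**Step 3: can Appendix 3 return an overall PR without CT/MRI lesions?** The table has no entry for absent CT/MRI disease, so three codings were tried.

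Coded as CT/MRI CR, there are 4 MIBG results (CR, PR, SD, PD) × 3 marrow results (CR, SD, PD) × 2 catecholamine results (normal, raised) = 24 combinations:

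| Overall result | Combinations |
|---|---|
| PD (MIBG PD: 6; marrow PD otherwise: 6) | 12 |
| SD | 8 |
| CR | 1 |
| No row | 3 |
| PR or VGPR | 0 |

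The three without a row are MIBG PR with marrow CR (catecholamines normal or raised) and MIBG CR with marrow CR and raised catecholamines. The SD text does not absorb them, because no site is SD.

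Coded as not applicable, none of the 12 non-PD combinations matches a row. Coded as SD, MIBG CR or PR with marrow CR matches no row. Overall PR is unreachable under all three codings. Appendix 3 does define PR for the MIBG component, but nothing carries it to the overall response.

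**Step 4: what is recorded.** Take a patient with no CT/MRI lesions, MIBG PR and marrow CR. Section 6.6.1 intends a responder. Section 4.5.5.2, under reading (a), gives a non-responder. Appendix 3 alone gives no result.

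**Step 5: size.** Table 3 states no error rate or derivation, so there is no figure to reproduce. For reference, P(at least 3 of 10 at 18%) = 1 − 0.82^10 − 10(0.18)(0.82^9) − 45(0.18²)(0.82^8) = 0.263. In a 10-patient cohort one affected patient moves ORR by 1/10, or 10 percentage points.

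The following is illustration only. Assume k of 10 patients lack CT/MRI lesions, a share s of responses is partial, and every such PR is lost. The recorded count is then Bin(10 − k, p) + Bin(k, p(1 − s)). With s = 0.75, P(at least 3) is:

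| True ORR p | k = 0 | k = 1 | k = 2 | k = 3 | k = 5 |
|---|---|---|---|---|---|
| 18% | 0.263 | 0.224 | 0.186 | 0.150 | 0.088 |
| 30% | 0.617 | 0.557 | 0.492 | 0.423 | 0.281 |
| 40% | 0.833 | 0.784 | 0.725 | 0.655 | 0.481 |

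With s = 0.50 and p = 30%, the values for k = 1, 2, 3 and 5 are 0.577, 0.535, 0.491 and 0.399. The documents give neither k nor s.

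**The case against.** The best defense is reading (b). If MIBG and marrow sites are measurable for neuroblastoma, Section 4.5.5.2 never reaches these patients. The eligibility wording is weak evidence against this, because it is one generic list for all tumor types. The separate evaluable category in Sections 3.4.4 and 6.6.1 is better evidence, since it would have little purpose if all such disease were measurable. The reach of Section 4.5.5.2 stays uncertain. The Appendix 3 gap stands on either reading.

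Two stronger inferences are tempting, and the documents do not support them.
- A reader might infer that ORR is biased downward. That follows only if Section 4.5.5.2 is applied to these patients. Under Appendix 3 alone the key cases are undefined, and an investigator might call them PR, SD or nothing. Inconsistent classification is shown; a downward bias is not.
- A reader might infer a material chance of a wrong expansion decision. The table above assumes both the number of affected patients and the loss of every PR. The protocol plans no formal hypothesis testing, says enrollment in a cohort may be stopped, and lets expansion also weigh feasibility, biomarker and safety data.

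It is also fair to say that Section 4.5.5.2 is not alone: Appendix 3 agrees with it in effect, so correcting that section by itself would not make PR assignable.

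**Conclusion.** The concern holds in this form. Section 4.5.5.2 contradicts the primary endpoint definition for neuroblastoma with evaluable disease, although the patients it covers are unclear. Independently, Appendix 3 cannot produce the PR that Section 6.6.1 counts when there are no CT/MRI target lesions. The neuroblastoma ORR and the count against 3 of 10 depend on which passage a site follows. The number of patients affected is unknown and may be zero. The definitional finding rests on the text alone; the probabilities rest on assumed shares and do not set its weight.

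A separate minor point concerns ATRT. A note in Appendix 11 makes SD the best possible response when only non-measurable disease is present. Sections 4.5.5.2 and 6.6.1 and the CR row of Appendix 11 itself allow CR.

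**What to change.** 1. In Section 4.5.5.2, exempt patients with neuroblastoma from the rule for evaluable but not measurable disease, matching Sections 3.4.4 and 6.6.1.
2. In Appendix 3, add an overall-PR entry, in the text and in Table 1, for patients with no CT/MRI lesions at baseline. Build it from the existing MIBG, marrow and catecholamine categories. It must give a result for the three unmatched combinations and for patients whose marrow was uninvolved at baseline.
3. In Sections 3.4.4 and 6.6.1, state that VGPR counts as at least a PR; both now name only CR and PR.
4. Settle this before the neuroblastoma initial response assessment and apply it to patients already assessed. The safety-evaluable denominator in Section 6.6 need not change.
5. Separately, reconcile the Appendix 11 note with Sections 4.5.5.2 and 6.6.1 and with the appendix's own CR row.

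The cost is an amendment, a sponsor decision on the PR rule, and re-review of existing MIBG, marrow and catecholamine records for any affected patients. No new procedures or visits are needed.
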